**Chi-square tests and logistic regression:**

- Quit attempts (prevalence of any quit attempts, yes/no)
- 7-day point prevalence abstinence (prevalence of any verified abstinence, yes/no)
- Adherence to NRT (prevalence of use of optimal amount of NRT, yes/no)
- Participant safety (prevalence of any adverse events, yes/no)

**t-tests and linear regression:**

- Change in CPD (measured as a continuous variable)
- Quit attempts (total number of quit attempts, measured as a continuous variable)
- Adherence to NRT (overall % of NRT used as directed, measured as a continuous variable)
- Participant safety (total number of adverse events, measured as a continuous variable)

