#### Secondary Outcomes:

- (1) Cigarettes per day (CPD) will be measured daily with the tracking feature embedded within each app. LTQ contains a feature that allows users to enter how many cigarettes they smoked at the end of the day
- (2) Quit attempts defined as self-reported no smoking at all for 24 hours, and time to 7-day relapse will be assessed via a Timeline Follow Back interview at Weeks 4, 8 and 12
- (3) 7-day point prevalence abstinence will be determined by responses to a standard self-report item (i.e., not smoking even a puff of a cigarette within the last 7 days) and breath CO<5 ppm at Week 12
- (4) Adherence to NRT will be measured daily with the app tracking feature, as well as brief interviewer-administered questionnaires at Weeks 4, 8, and 12
- (5) Participant Safety will be assessed by monitoring all adverse events during the 12-week period and in close collaboration with their medical providers

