- **Timeline Follow-Back:** This measure quantifies the substances a subject has used in a certain period of time. It utilizes a calendar format and key events to record substance use. In our trial, we will specifically be asking about cigarette consumption, smoking abstinence, NRT usage, and Antiretroviral Therapy (ART) adherence. Depending on the timeframe of the assessment, the measure takes about 10 minutes to complete.
- **Smoking Abstinence Survey:** This is a brief 12-item questionnaire designed to assess current smoking or non-smoking behavior, including quit attempts and periods of abstinence. It also includes questions about NRT use. This measure takes approximately 3 minutes to complete.
- **Systems Usability Scale:** A 10-item questionnaire, measuring various metrics of usability of a design using a 5-point Likert Scale. We complete these with subjects at each follow-up. This measure takes approximately 2 minutes to complete.
- **Research Participant Perception Survey:** Questionnaire used to assess the research participation experiences of participants to help the research team potentially improve the experience of clinical trial research participants. We are using a shortened 13-item version of the original 77-item measure. Research staff will provide the survey to the participant at the end of their study participation. Participants will enter this information in directly in order to avoid social desirability effects. This measure takes approximately 2 minutes to complete.

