### 6.3. Baseline Visit

Participants will attend a Zoom baseline session following their eligibility determination to be randomized to the intervention. A few measures will be completed prior to randomizing the participant:

- (1) Health Changes questionnaire (adverse event and con med forms filled out if applicable)
- (2) COVID-19 & Quitting smoking Questionnaire (Adapted)
- (3) Assessing psychiatric functioning
  - a. Depression Anxiety Stress Scale-21 (DASS-21)
  - b. C-SSRS
  - c. Brief Symptom Inventory (BSI)
- (4) Fagerström Test for Nicotine Dependence (FTND)
- (5) Timeline Follow-Back (TLFB) Questionnaire
- (6) Drug Use Questionnaire (1 Month)
- (7) Internet/Smartphone Access and Use survey

After completing these measures, the participant will be randomized. They will receive either the LTQ-H app, or a standard-of-care app called QuitGuide developed by the National Cancer Institute (NCI). The RA will instruct

the participant on how to download their assigned app from the App Store/Google Play Store. The RA will give a brief overview of the assigned app to discuss the main functions and troubleshoot any major issues that may arise. They will also instruct the participant to enter their unique tracking code (similar to their subject ID) to allow us to track their background analytics data.

Following the baseline visit, we will mail 8 weeks of NRT patches to participants. We will tell participants to call/email the study team to confirm that they received their NRT. We will then instruct participants to start using the patches on the day of their quit date, which will be within 4 weeks of the baseline visit. Participants will be oriented on the best practices of using NRT based on the package instructions. There will be a brief compliance review session following the instructions in order to ensure that patients understand how to use the medication.

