#### Secondary outcome measures include:

- Change in cigarettes smoked per day (CPD) (measured daily with the tracking feature embedded within each app)

- Quit attempts (self-reported no smoking at all for 24 hours—and *time to 7-day relapse* will be assessed via a Timeline Follow Back interview at Weeks 4, 8, and 12)
- 7-day point prevalence abstinence (not smoking even a puff of a cigarette within the last 7 days) and breath CO<5 ppm at Weeks 4, 8, and 12)
- Adherence to NRT (measured via app tracking feature and Timeline Follow-Back interview at Weeks 4, 8, and 12)
- Participant safety (adverse events)

Differences between treatment groups (LTQ-H vs. NCI QuitGuide) in terms of secondary outcomes will be assessed via chi-square tests and logistic regression or t-tests and linear regression, as appropriate:

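### Change in cigarettes per day has no named baseline and no prespecified covariate, although pre-randomisation Timeline Follow-Back data could supply both and would usually narrow the interval

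*Combined protocol and SAP*

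**What the plan says.** Section 8.2 gives the outcome as "Change in cigarettes smoked per day (CPD) (measured daily with the tracking feature embedded within each app", and Section 2.2 gives the same source: "Cigarettes per day (CPD) will be measured daily with the tracking feature embedded within each app". Differences between arms in the secondary outcomes "will be assessed via chi-square tests and logistic regression or t-tests and linear regression, as appropriate". Under the t-test and linear regression list, the CPD entry is only "Change in CPD (measured as a continuous variable". Section 8.2 states no model terms, covariate, baseline or follow-up time point for CPD.

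Section 6.3 fixes the order of events at the baseline visit. The measures done first include the "Timeline Follow-Back (TLFB) Questionnaire". Then: "After completing these measures, the participant will be randomized". Only afterwards is the participant shown "how to download their assigned app from the App Store/Google Play Store". Section 5.2 says of the TLFB that "we will specifically be asking about cigarette consumption", among other things, and leaves its timeframe open. Section 6.4 repeats the TLFB at Weeks 4, 8 and 12.

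Section 5.1 uses a baseline CPD value to choose the patch course. It names no source for that value and does not link it to the outcome analysis.

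**The concern.** Two things are left open.

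- **The baseline.** A change score needs a starting value, and the named source has none before randomisation. The analyst could take the TLFB, the unsourced value used for the patch course, or the first in-app entries. These are not interchangeable. The first two appear to predate the intervention. The third would follow it, so the arm difference in change would then estimate the later effect minus any early effect.
- **The covariate.** Linear regression can include baseline CPD, but Section 8.2 does not say that it will. If the comparison is a plain t-test on change, its interval will usually be wider than the collected data allow. Section 8.1 justifies the sample size by precision and confidence intervals rather than power, so interval width is a relevant yardstick here.

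**Working it through.** **The plan's own figures.** There is none for CPD. The only power statement (Section 8.1: 70%, 75% and 80% at effect sizes 0.32, 0.34 and 0.36) concerns abstinence. It reproduces as a 1-df chi-square test with Cohen's w, N = 60 and an assumed two-sided alpha of 0.05: 69.8%, 75.0% and 79.6%. It has no bearing on this point.

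**Inputs.** From the documents: 30 per arm, 1:1. Assumed, because the documents do not give them: rho, the correlation of baseline and follow-up CPD; and k, the follow-up SD divided by the baseline SD.

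**Formulas**, in units of the baseline SD, with f = 1/n1 + 1/n2 and N = n1 + n2:

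- Unadjusted change: variance = (1 + k² − 2·rho·k)·f, with t on N − 2 df.
- Baseline-adjusted (ANCOVA): variance = k²·(1 − rho²)·f·(1 + 1/(N − 4)), with t on N − 3 df. The last factor is the cost of estimating the slope.

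**Worked case**, k = 1, rho = 0.5, 30 per arm, f = 0.0667:

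- Change: variance 1.00 × 0.0667 = 0.0667; half-width 2.0017 × √0.0667 = 0.517.
- ANCOVA: variance 0.75 × 0.0667 × (1 + 1/56) = 0.0509; half-width 2.0025 × √0.0509 = 0.452.
- 1 − 0.452/0.517 = 12.6% narrower.

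**Reduction in 95% CI width, ANCOVA against change score, 30 per arm** (negative means wider):

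| rho | k = 0.75 | k = 1 | k = 1.25 |
|---|---|---|---|
| 0.1 | 36.6% | 25.2% | 17.5% |
| 0.3 | 31.5% | 18.6% | 10.6% |
| 0.5 | 27.3% | 12.6% | 4.6% |
| 0.7 | 24.5% | 7.0% | 0.0% |
| 0.75 | 24.3% | 5.6% | −0.6% |
| 0.8 | 24.6% | 4.3% | −0.9% |
| 0.85 | 25.6% | 2.9% | −0.5% |
| 0.9 | 28.4% | 1.6% | 1.6% |

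**Where the gain disappears.** The slope of follow-up on baseline is rho·k. At k = 1.25 and rho = 0.8 it is exactly 1. The change score then already subtracts the right amount: 1 + 1.5625 − 2 = 0.5625 equals 1.5625 × 0.36 = 0.5625. Only the estimation cost remains, 1 + 1/56 = 1.018 in variance, or 0.9% in width.

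**With losses.** As an illustration, apply the 93% and 70% retention figures in Section 8.1 to 30 per arm: 27.9, taken as 28, and 21. At k = 1 the interval is 18.4%, 12.4%, 6.7% and 1.4% narrower at rho 0.3, 0.5, 0.7 and 0.9. The worst case on the grid, k = 1.25 and rho = 0.8, is 1.2% wider.

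**Low rho.** A TLFB covariate may correlate only weakly with an in-app outcome. At k = 1 and rho 0.1, ANCOVA is 0.4% wider than a t-test on follow-up alone; at rho 0.2 it is 1.1% narrower. So at low rho nearly all the gain over change comes from no longer subtracting a weakly related baseline.

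**Bias.** With a pre-randomisation baseline, randomisation makes expected baseline CPD equal between arms, so both methods estimate the same difference. The comparison above is of precision only.

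**The case against.** The strongest reply is that the plan already allows the better model. Linear regression on arm alone reproduces the equal-variance t-test, so naming both plausibly leaves room for covariates. The TLFB, done at the baseline visit, is a natural baseline. Section 8.1 expects wide intervals and says the trial's relevance does not rest on estimating population parameters. CPD is one of five secondary outcomes. The size of the gain is wholly assumed.

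Most of this stands, and it limits the point to under-specification with a small consequence. It does not remove it: allowing adjustment still leaves the choice of covariate and baseline until the data are in hand.

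A reader might infer three stronger things that the documents do not support:

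- That the planned analysis is biased or excludes adjustment. It does neither, provided the baseline precedes randomisation.
- That early in-app entries will serve as the baseline. No section proposes this. It is only a possibility that the wording does not close off.
- That QuitGuide cannot supply CPD. Its description in Section 5.1 lists smoke-free and slip days but no cigarette count. However, Section 2.2 says CPD is tracked within each app, and Section 6.4 includes CPD in the background analytics. The sections need reconciling; they do not show that the data are absent.

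**Conclusion.** The point holds as a minor one. Section 8.2 leaves the baseline for change in CPD and any covariate unspecified, while suitable pre-randomisation data are already scheduled.

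The precision gain cannot be fixed from the documents. Over rho 0.1 to 0.9 with 30 per arm, the adjusted interval is about 24% to 37% narrower if the follow-up SD is 0.75 times the baseline SD, and about 2% to 25% narrower if the SDs are equal. If the follow-up SD is 1.25 times the baseline SD, it runs from 17.5% narrower to about 1% wider. Adjustment is therefore usually, but not always, more precise, and the possible loss is negligible. The primary outcomes, the sample size and the stated abstinence power are unaffected.

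**What to change.** Replace the CPD entry in Section 8.2 with wording such as:

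> CPD at Week 12 (mean over a window of days fixed in advance, source stated) will be compared between arms by linear regression on treatment arm, with pre-randomisation TLFB CPD (mean over a look-back window fixed in advance) as a prespecified covariate. The adjusted mean difference and 95% CI will be reported. Any unadjusted comparison of change will be supplementary and will use TLFB CPD at both baseline and Week 12.

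The covariate need not come from the same instrument as the outcome, so in-app CPD may stay as the outcome source if both apps record it. A change score should not subtract TLFB from in-app counts, hence the last sentence. Before finalising, either confirm that QuitGuide records a daily cigarette count or make Week 12 TLFB CPD the outcome source and align Section 2.2.

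The cost is a few sentences, two windows to fix in advance and one degree of freedom. No new data are needed, because the TLFB is already scheduled before randomisation and at Week 12. The statistical downside is an interval at most about 1% wider over the range examined.

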## 4.0. Study Overview

- 1. Eligibility and Consent:** PLWH who provisionally qualify based on a phone screen will be invited to attend a remote Zoom screening visit. Informed consent will be obtained, and participants' interest in quitting, HIV and smoking statuses will be evaluated. Individuals will be screened to ensure that they own an Apple or Android smartphone, are not pregnant (if female), and are medically eligible to use NRT. Our study physician will evaluate their medical eligibility. In addition, we will obtain a signed Release of Information from potential participants to closely work with their own medical providers to monitor adverse events, dispensing of NRT, and overall participant safety.
- 2. Randomization:** Participants will be allocated to conditions using 1:1 randomization.
- 3. Interventions:** Participants will be assigned to LTQ-H or NCI QuitGuide. All participants will receive a standard 8-week course of NRT (transdermal nicotine patches starting at 21mg/24h) following recommendations contained in the U.S. Clinical Practice Guidelines.
- 4. Background Analytics:** Research staff will instruct participants on how to install the study app onto their personal smartphones and will tell them how to add a study ID in the app that will be used to retrieve background analytics information (Google Analytics) from both the LTQ-H and NCI QuitGuide apps.
- 5. Follow-Up Visits:** Visits will occur at 4, 8 and 12 weeks post-randomization. During these visits we will assess smoking and smoking abstinence, new or changes in existing adverse events and user experience with the assigned app. We will biochemically verify self-reported smoking abstinence at week 12.

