#### 6.4. Follow-Up Visits

Participants will complete monthly follow-up (FU) visits at Weeks 4, 8, and 12 weeks post-randomization. All visits will be conducted via zoom video calling.

At each visit, participants will complete surveys to assess their smoking behavior, changes in physical or mental health (which will prompt staff to assess for adverse events), and user experience with their assigned study app. See table below for a list of all the measures.

At each visit, research staff will conduct an interview with the participant to ask about their experience using their assigned app. This interview will be audio recorded for later review. Each FU visit is expected to last between 45-60 minutes, depending on the assessment burden.

Measure	Week 4	Week 8	Week 12
Biochemical Verification (CO)			x
Health Changes Questionnaire	x	x	x
Adverse Events and Con Meds (if applicable)	x	x	x
COVID-19 & Quitting Smoking Questionnaire (Follow-up)	x	x	x
Drug Use Questionnaire (1 Month)	x	x	x
Timeline Follow-Back	x	x	x
DASS-21	x	x	x
BSI	x	x	x
Systems Usability Scale (SUS)	x		x
Qualitative user experience interview	x		x
Research Participant Perception Survey (RPPS)			x

Participants who self-report smoking abstinence by the final follow-up visit (FU3) will be mailed an iCO smokerlyzer device to do a breath test in order to biochemically verify abstinence. We will mail these to participants following their FU3 session. Once they receive the device, we will set up a short Zoom call to walk them through the CO breath test process. Staff will be on the call in order to ensure that it is the participant

who is doing the test, and that they are doing the test properly. Once the participant completes the test, we will ask them to email the result of their test to our lab email. Participants will keep these devices once they are completed in the study. The stop date for these participants will be the date of this breath test instead of the date of the FU3 visit.

Background analytics will be collected throughout the 4 months of participation, and will be measuring some things such as CPD, mood ratings, NRT use, duration of app use, and number of interactions within the app.

At the final visit (Week 12), participants will be given quitting resources if they have not quit. They will also be referred to other research studies, if eligible and willing.

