## 8.0. Data Analysis and Sample Size

### 8.1. Determination of Sample Size

Given that this is primarily a feasibility and acceptability trial, we expect the intervention effect sizes to have notable variance (i.e., wide confidence intervals), thus the relevance of the current study is linked to its significance and potential impact to the field, and not on its ability to estimate parameter estimates in the population. In this scenario, a precision (rather than power) approach is especially suited, since calculating confidence intervals is ideal for preliminary or pilot investigations, and facilitates that sample size is determined by practical rather than formal considerations. Given that retention is a key issue in smoking cessation studies, we will focus on this primary outcome. A pilot study of LTQ and prior studies in the general population of ACT-based interventions for smoking cessation show 93% 6-month participant retention, and 70% for standard of care.

Further, with 30 participants per group, we calculated that we would have 70%, 75% and 80% power to detect abstinence rates of 0.32, 0.34, and 0.36 effect sizes, respectively.

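### Change in cigarettes per day is tested as one undefined value per person; a baseline-adjusted repeated-measures model on the Timeline Follow-Back data would use all visits and guard better against drop-out

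*Combined protocol and SAP*

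**What the plan says.** **Analysis.** Section 8.2 says that arm differences in secondary outcomes "will be assessed via chi-square tests and logistic regression or t-tests and linear regression, as appropriate". The CPD entry, under the t-test and linear regression list, is "Change in CPD (measured as a continuous variable". Section 8.2 gives no start point, end point or averaging window for the change. It names no repeated-measures model, analysis population or missing-data rule. Trajectories are planned only for app engagement, and only as plots.

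**Source of CPD.** Sections 2.2 and 8.2 name the app: "Change in cigarettes smoked per day (CPD) (measured daily with the tracking feature embedded within each app". Section 5.1 describes daily cigarette entry in LTQ-H. For QuitGuide it describes mood, craving and smoke-free or slip-day tracking, but no daily cigarette count.

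**Other smoking data.** For TLFB, Section 5.2 states: "In our trial, we will specifically be asking about cigarette consumption, smoking abstinence, NRT usage". Section 6.3 lists TLFB at baseline and the table in Section 6.4 lists it at Weeks 4, 8 and 12.

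**Retention.** Section 8.1 treats retention as a key issue and reports that a pilot of LTQ and earlier studies of related interventions "show 93% 6-month participant retention, and 70% for standard of care".

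**The concern.** A t-test takes one number per person. If that number is the Week 12 value minus baseline, anyone without a Week 12 value leaves the comparison, even with one or two earlier follow-up values on file. Section 8.1 itself makes unequal loss foreseeable. If people who are smoking more are likelier to leave, and more people leave QuitGuide, the QuitGuide completers will look better than the arm as randomised, and the contrast will run against the app under test.

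Because the end point is open, completer change, last value or period average could also be chosen after the data are seen. Preliminary efficacy is a stated goal (Section 2.1), and the timeline in Section 4.1 puts preparation of a larger trial's grant application in the same months as the analysis. A distorted CPD contrast could therefore carry forward.

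**Working it through.** The documents give no power, precision or bias figure for CPD, so there is none to reproduce.

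**1. Loss implied by the cited retention.** 30 × 0.93 = 27.9 and 30 × 0.70 = 21.0 people remain: about 2 lost against 9, or 7% against 30%.

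**2. When a completer change score is biased.** Suppose drop-out depends on CPD at visit k, so that completers' mean CPD at that visit lies m below the mean of the arm as randomised. With equal SDs and linear relations, their baseline mean shifts by ρ(0,k)·m and their Week 12 mean by ρ(k,12)·m. The bias in LTQ-H minus QuitGuide is

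[ρ(k,12) − ρ(0,k)] × (m_QuitGuide − m_LTQ-H).

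It is zero if drop-out is unrelated to smoking (both m are 0), if selection is the same in both arms, or if the correlations are equal. With ρ(8,12) = 0.8 and ρ(0,8) = 0.45 the multiplier is 0.35; with ρ(4,12) = 0.7 and ρ(0,4) = 0.5 it is 0.2.

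**3. Simulation, true difference zero.** Assumed, because the documents do not give them: CPD means 15, 11, 10, 10 at baseline and Weeks 4, 8, 12 in both arms; SD 8; baseline correlations 0.5, 0.45, 0.4; correlations between follow-ups 0.7 to 0.8; loss 7% against 30%, after Week 4 or Week 8. OR is the odds ratio of drop-out per 8 cigarettes. Bias (400,000 per arm) is LTQ-H minus QuitGuide in CPD. The last column is the completer t-test's rejection rate at nominal 5% (6,000 trials of 30 per arm).

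| Drop-out depends on | Completer change | Baseline-adjusted regression | Likelihood, all visits | Rejection |
|---|---|---|---|---|
| nothing (random within arm) | −0.01 | −0.02 | 0.00 | 5.2% |
| last CPD, OR 2 | 0.34 | 0.73 | −0.01 | 4.8% |
| last CPD, OR 3 | 0.51 | 1.05 | 0.02 | 5.8% |
| change so far, OR 2 | 1.06 | 0.69 | −0.05 | 6.9% |
| change so far, OR 3 | 1.57 | 1.03 | 0.03 | 9.0% |
| unseen change, OR 2 | 1.34 | 0.93 | 0.41 | 7.6% |
| unseen change, OR 3 | 1.80 | 1.27 | 0.59 | 11.4% |
| change so far, OR 3, equal 18.5% loss | −0.04 | −0.04 | −0.03 | 4.8% |

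The completer standard error at 30 per arm was 2.4 to 2.6.

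**4. Sensitivity to the correlations.** With all correlations 0.6 and drop-out on last CPD, completer change bias was −0.02, as step 2 predicts, baseline-adjusted bias 0.31 to 0.43, and likelihood bias −0.02 to −0.03. With drop-out on the unseen level, completer change gave 0.27 to 0.33 and the likelihood model 0.47 to 0.65, so the model does not win in every setting.

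**5. Second check, with the covariance estimated in each trial of 30 per arm** (SD 8, 7% against 30% loss). With drop-out following observed smoking, bias was about 0.3 to 1.3 for completer change, about 0.8 for baseline-adjusted regression and about 0 for the likelihood model. With drop-out random within arm, no method was biased.

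**6. Precision.** In the second check the model's standard error was about 19% below the change-score t-test and about 5% below baseline-adjusted regression. Most of the 19% is baseline adjustment: at a baseline to Week 12 correlation of 0.4, √[(1 − 0.4²)/(2 − 2 × 0.4)] = √(0.84/1.20) = 0.84, a 16% reduction. The earlier visits add the rest.

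**The case against.** A reader might infer that the plan discards the Week 4 and Week 8 data or restricts CPD to completers. The documents do not say so. Section 8.2 fixes no end point; a last-value or whole-period change would use early data and could still be t-tested. The loss of early data is a consequence of one natural reading.

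A reader might also infer that unequal drop-out by itself biases the test. It does not: random loss of 7% against 30% gave no bias.

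Further points stand in part:

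- The 93% and 70% are 6-month figures from earlier studies. Here follow-up lasts 12 weeks, both arms receive patches and the same visits, and the largest payment comes at Week 12. A smaller gap would give a smaller bias.
- The named CPD source is the app, and Sections 2.2 and 8.2 assign TLFB to other outcomes. Moving to TLFB is a real change and must be stated. It is also the safer source, because TLFB is scheduled identically in both arms.
- Linear regression is already listed and allows baseline adjustment. That recovers most of the precision, but leaves about 0.7 to 1.1 CPD of bias in step 3 when drop-out follows observed smoking.
- Quit dates may fall up to 4 weeks after baseline (Section 6.3), so Week 4 TLFB may largely describe smoking before quitting. With visit-specific arm effects, Week 4 only helps to predict missing Week 12 values and does not enter the reported contrast directly.
- Section 8.1 says that the study's relevance does not rest on parameter estimation. That limits the importance of the point but does not justify leaving the end point open.

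**Conclusion.** The point holds in conditional form. Section 8.2 tests one undefined CPD change per person and makes no planned use of the repeated smoking data. Run as a Week 12 change score, it drops early leavers. If drop-out both differs by arm and is related to smoking, the contrast is biased by roughly 0.3 to 1.3 CPD against LTQ-H, about 0.04 to 0.16 of the assumed SD (0.3/8 to 1.3/8) and 0.1 to 0.5 of a standard error of 2.5.

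The size rests on the assumed SD, correlations, drop-out mechanism and 7% against 30% loss. Equal correlations with drop-out on CPD level give none; the strongest observed-data mechanism in step 3 gives 1.6. The repeated-measures model removes the bias only when drop-out depends on observed data. The change is worth making because it is cheap and uses data already scheduled, but CPD is secondary in a 60-person pilot.

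**What to change.** In Section 8.2:

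1. **Define the outcome.** Name TLFB as the CPD source for this analysis and fix one averaging window for baseline and for each visit. Reconcile Sections 2.2 and 8.2, which rely on CPD tracking in each app, with Section 5.1, which describes no daily cigarette count in QuitGuide. If QuitGuide has none, app-based CPD would be missing by arm even among people who stay.
2. **Fit a linear mixed model** to TLFB CPD at Weeks 4, 8 and 12, with arm, visit and arm-by-visit, unstructured covariance and Kenward-Roger degrees of freedom. Bring in baseline TLFB CPD either as a covariate or as a repeated outcome with a common baseline mean; the second form keeps people with no follow-up. Report the Week 12 arm difference with its confidence interval.
3. **Keep the t-test as a check**, labelled as such, with the number analysed per arm.
4. **Add a sensitivity analysis for drop-out related to unobserved smoking.** For example, raise the predicted Week 12 CPD of leavers by d cigarettes in both arms. At 7% against 30% loss, LTQ-H minus QuitGuide moves by (0.07 − 0.30) × d = −0.23d. Report a range of d.

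The cost is SAP wording and a standard model, with no extra visits or measures. The downside is the assumption that drop-out depends only on observed data, which item 4 examines.
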